1.0 Study Summary

Study Title	R01 FX ENTRAIN: Perturbation of Neurodynamics Underlying Sensory Hyperarousal and Statistical Learning in Youth with FXS
Study Design	The proposed project includes a case-control descriptive study (Aims 1 & 2) and an acute, crossover clinical trial (Aim 3).
Primary Objectives	Aim 1: Translational neurodynamics in resting and sensation. Aim 2: Cognitive studies (Statistical Learning). Aim 3: Sensory and cognitive perturbation studies.
Research Intervention	Closed-loop alpha auditory entrainment
Study Population	The study population includes subjects 5 to 15 years of age with Fragile X Syndrome (FXS) with full FMR1 mutations, as well as two age-and-sex matched cohorts of control subjects consisting of typically developing controls (TDC) and subjects with autism spectrum disorder (ASD).
Sample Size	180 human subjects will be recruited in total: 120 subjects total for case-control portion (60 FXS, 60 ASD, 60 TDC) and 60 subjects total for clinical trial (20 FXS, 20 ASD, 20 TDC).
Study Specific Abbreviations/Definitions	FXS, Fragile X Syndrome KO, knockout TDC, typically developing control AAE, alpha auditory entrainment EEG, electroencephalography ITC, inter-trial coherence ASD, autism spectrum disorder FMRP, Fragile X mental retardation protein CFC, cross-frequency power-power coupling ERP, event-related potentials TCD, thalamocortical dysrhythmia SL, statistical learning PAF, peak alpha frequency PPF, peak power frequency WT, wild type BCI, brain-computer interface WLI, word learning index BLE, behavior learning effect AM, amplitude modulated LSS, lab streaming layer (software component) GUID, global unique identifier NDAR, National Database for Autism Research NIMH, National Institute of Mental Health ERSP, event-related spectral power CNS, central nervous system

2.0 Objectives

Our **central hypothesis** is that in Fragile X Syndrome (FXS), reduced alpha (~10 Hz) pacing and increased gamma (>30 Hz) noise impairs, via altered timing, the detection of sensory patterns and the ability to mount precise neural responses, thereby impeding cognitive functioning and contributing to increased sensory hypersensitivity. Our **approach** involves three scientific aims, which, if addressed, would ascertain underlying mechanisms that may alleviate sensory and cognitive impairments.

Specific Aim 1: Translational neurodynamics in resting and sensory studies. We hypothesize that fine-temporal alpha and gamma neurodynamics will uncover the basis of participant- and subgroup-level variation that drives FXS group effects. **1A:** We will acquire resting-state electroencephalography (EEG) and sensory auditory chirp paradigms in 40 youth (5 to 15 years old) with FXS and age- and sex-matched typically developing controls (TDC) and autism spectrum disorder controls (ASD). Neurodynamics (peak power frequency, spectral events) and biophysical modeling of each paradigm will be compared between groups. Neurodynamics will be assessed individually and in combination as predictors of psychological measures, medication effects, co-occurring neuropsychiatric diagnoses, and computerized cognitive testing. **1B:** We aim to identify neurodynamic features that distinguish *Fmr1^{-/-}* KO from wild type (using preexisting resting-state EEG and sensory auditory chirp murine data). **1C (Exploratory):** We aim to identify neurodynamic features that are conserved between *Fmr1^{-/-}* KOs and participant human subgroups based on genotype. We hypothesize that full mutation, non-mosaic males with FXS will share similar neurodynamics as the *Fmr1^{-/-}* KO (knockout) mouse. Shared neurodynamics between *Fmr1^{-/-}* KO and a human subgroup will have a high translational impact.

Specific Aim 2: Cognitive studies. We hypothesize statistical learning (SL) will be impaired in FXS and the degree of SL impairment will be related to cognitive and language abilities in FXS. **2A:** Passive SL Task will compare structured (word) entrainment via EEG intertrial coherence (ITC) between FXS, TDC, and ASD. **2B:** Psychological measures (i.e., cognitive testing, expressive language sampling, and language ability) will be examined to identify key subgroups and predictors of neural response. As the Passive SL Task can capture an objective proxy of a cognitive process across a wide variety of functional levels, it will have a high impact on understanding heterogeneity in FXS.

Specific Aim 3: Sensory and cognitive perturbation studies. We hypothesize that “bottom-up” alpha auditory entrainment of the corticothalamic drive will normalize the ability to mount precise neural responses to stimuli (increased ITC) and diminish asynchronous gamma “noise.” **3A:** Acute perturbation with closed-loop (to individualize stimulus) alpha auditory entrainment (AAE) will be conducted in FXS and sex- and age-matched TDC and ASD controls (n=20 per group). AAE will be performed in two visits as a double-blind, sham-controlled crossover study such that each participant will receive AAE and sham in random order. We will assess if closed loop AAE leads to normalizing phase synchronization of the sensory auditory chirp and the Passive SL Task. **3B (Exploratory):** We will determine if AAE can enhance word learning as measured by reaction time in the Active SL Task.

3.0 Background

Fragile X Syndrome (FXS), a monogenetic neurodevelopmental disorder, manifests varying levels of intellectual disability, autistic features, and sensory hypersensitivity¹. To date, despite over 60 publications of phenotypic rescue in animal models, pharmacological and behavioral treatments have yielded little clinical success in improving cognitive symptoms in FXS in human trials^{2, 3}. Central to this discrepancy is a poor understanding of the constituent neurodynamics of averaged group effects and individual variability in human brain activity as related to higher-level cognitive symptomatology and clinical phenotype^{4, 5}. This could, in part, account for the major discordance between mouse and human drug treatment effects. Additional factors including development, environment, and medications can further meaningfully contribute to heterogeneity. In large, published cohorts, we and others have identified reproducible, group-level abnormalities in resting-state EEG and sensory auditory chirp responses linked with intellectual disability, neuropsychiatric symptoms, and sensory

hyperarousal⁶⁻¹⁴. This data demonstrates that individuals with FXS do not mount precise neural responses to the sensory auditory chirp and, instead, show increases in “noise” in the form of asynchronous gamma activity¹⁰. Furthermore, a marked reduction in alpha power suggests altered thalamocortical function, reducing the ability to detect signal from noise in the environment and representing potential tractable targets for “bottom-up” entrainment. However, to translate these findings to effective treatments for individuals with FXS, two significant knowledge gaps must be addressed: 1) how does individual variability in neural activity in FXS contribute to core, impairing sensory and cognitive symptoms; and 2) could individually targeted, external entrainment of this neural activity improve sensory and cognitive function?

[figure not shown]
Significance of Aims

Constituent Neurodynamics of Alpha and Gamma Alterations (Aim 1):

Despite being a single-gene disorder, FXS patients exhibit marked variability in EEG, molecular, and behavioral phenotypes compared to the Fmr1-/-KO mouse model^{6, 15-18}. This high variability is observed within and across males with full mutation (mosaic and non-mosaic) and females who, due to an X-linked disorder, exhibit obligate mosaicism^{7, 15, 19, 20}. Though a link between Fmr1-/-KO and males with full mutation FXS can be predicted based on suspected Fmr1 expression²¹, the degree to which they share conserved physiology is yet unknown. Identifying parallel neurophysiological markers between mice and a particular human subset would represent a significant breakthrough for precision medicine in FXS. EEG is a highly feasible method to postulate whole-brain hypotheses in FXS, for which there is consensus on group-level effects in humans^{8-10, 14} and Fmr1-/-KO mice^{6, 22, 23}. Therefore, Aim 1 studies will investigate the neurodynamic basis and biophysical modeling of alpha and gamma alterations in resting-state and sensory auditory chirp EEG¹⁷ to parse heterogeneity.

Statistical Learning as a High-value Target in FXS (Aim 2): Though resting-state and sensory studies can provide insight into FXS physiology, there is an urgent need to develop cognitive paradigms that can be studied across the FXS phenotype and be broadly applicable to cognitive development. Children with FXS, for example, do not keep pace with the typical rate of cognitive development, and their skills plateau prematurely²⁴. Statistical learning (SL) is the process by which humans extract patterns in sensory input, through passive exposure and without effort or conscious intention to learn. SL is present from birth²⁵ and operates continuously across the lifespan to extract and flexibly update statistical regularities from the environment²⁶. While SL operates across many different domains, it is thought to play a significant role in language learning, most notably in speech segmentation²⁷. Pauses or other acoustic cues do not reliably demarcate words in continuous speech. Becoming sensitive to the statistical regularities between neighboring syllables may allow learners to discover word boundaries in speech^{28, 29}. Given most individuals with FXS show significant, lifelong language impairments, including delay of first words, deficits in SL would be expected in FXS²⁷. Confirming this hypothesis and determining whether intervention is effective at improving SL would have far-reaching clinical implications, as improving communication abilities is an almost ubiquitous goal for families of individuals with FXS³⁰.

Since SL is performed passively and can be measured through EEG independently of behavior, it can be captured in children with FXS regardless of cognitive functioning ability^{31, 32}. During SL, complex patterns are passively extracted through environmental exposure. Interestingly, the neural acquisition of patterned data heuristically resembles the responses to sensory auditory chirp when monitored by EEG and can similarly be quantified using inter-trial coherence (ITC)³¹. In this regard, SL is an ideal bridge between passive EEG sensory

paradigm like the sensory auditory chirp and more complex but less feasible cognitive or language EEG paradigms (**Fig. 4**).

Normalizing EEG through Alpha Auditory Entrainment (AAE) (Aim 3): The observed reproducible alterations in brain activity raise a key question: would normalization of targeted EEG activity lead to improved sensory and SL markers within the disorder? Thus far, it remains an open question whether the EEG alterations observed in FXS represent a physiological mechanism that maintains suboptimal brain states or if they simply reflect compensatory changes to other aberrant neural processes. Though previous reports have identified group-level correlations of EEG and behavioral data, the ability of AAE to “pace” alpha rhythms (10 Hz) into typical range can be directly quantified by online monitoring of real-time EEG. If successful, this could lead to a new approach to addressing the underlying cognitive impairment in FXS and thus alter the trajectory of intellectual development in this disorder².

Summary: To this end, we have developed a cutting-edge approach to study heterogeneity in EEG signatures in humans, explore their relevance for sensory and cognitive disturbances, and introduce perturbation studies to test causal inferences. Our approach encompasses three key areas that, in our opinion, are of critical importance to advancing the FXS field. First, we will perform fine-temporal analysis (neurodynamics) of resting-state and sensory EEG to capture individual variability, model biophysical properties, and quantify the constituent factors of known group effects. At this juncture, we also ascertain which subgroup of persons with FXS shares neurodynamic profiles with the Fmr1-/-KO mouse model. Second, we will study SL in FXS as a cognitive proxy and identify neural markers of SL with individual and subgroup variability. Third, we propose to move beyond correlational studies to examine causal effect, for the first time, that if individualized alpha entrainment will lead to normalization of neural responses in response to sensory auditory chirp and SL word entrainment.

Preliminary Data Justifying Proposed Approach

The investigative team has collected the largest cohort to date of high-resolution FXS patient resting-state EEGs (n=70; 32F; mean age= 20.5+/-10 years old; range=6 to 46) with age/sex-matched controls (n=71; 30F; mean age=22.2+/-10.7 years old; range=6-48). We recently conducted the first source analysis of resting-state EEG in FXS and found 1) decreased peak alpha frequency, 2)

reduced alpha power, 3) centralized distribution (known as anteriorization) of “slow” alpha frequencies (8 to 10 Hz), 4) theta power, not alpha power, is inversely coupled to gamma power in FXS, and 5) increased asynchronous gamma power (see **Fig. 5** for summary)³³.

[figure not shown]

Fig. 5: Alterations in resting EEG (FXS, n=70; TDC, n=71). **A**) shift of peak alpha frequency towards the theta frequency and a decrease in alpha power. **B**) marked cortical alpha reduction (left) and alpha slowing and “anteriorization” (right) in FXS suggests decreased thalamocortical drive. **C**) increased theta power (left), centralized distribution (known as anteriorization) of “slow” alpha frequencies (shown in **Fig. 2B**), increased asynchronous gamma activity (right). We propose to test the hypothesis that auditory alpha entrainment can enhance thalamocortical signaling to enhance alpha activity and decrease asynchronous gamma. (TDC, typically developing controls; M, male; F, female).

Global decrease and “slowing” of alpha activity in FXS: A peak frequency of 10 to 13 Hz (upper alpha) has specific functional relevance for several major physiological systems in typically developing individuals³⁴⁻³⁸. As a radio receiver prefers specific electromagnetic frequencies, neurons and oscillatory networks also demonstrate frequency preferences^{39, 40}. The “switch” to a dominant peak rhythm at 4-8 Hz in FXS (**Fig. 5A**) and reduced global alpha power (**Fig. 5B**) may be insufficient to drive neural ensembles with an alpha preference^{35, 38, 41, 42}. Thus, the canonical role of alpha in

establishing inhibition-timing windows for optimal sensory and neurocognitive processing may be impaired in FXS.

The peak frequency of 10 to 13 Hz (upper alpha) is functionally important for several physiological systems in typically developing individuals³⁴⁻³⁸. Like a radio receiver, neurons and oscillatory networks also demonstrate frequency preferences^{39, 40}. In FXS, there is a "switch" to a dominant peak rhythm at 4-8 Hz (theta range) and reduced global alpha power, which may be insufficient to drive neural ensembles with an alpha preference^{35, 38, 41, 42}. Thus, the canonical role of alpha in establishing inhibition-timing windows for optimal sensory and neurocognitive processing may be impaired in FXS.

Noisy Elevated Gamma in FXS (**Fig 5C**): Asynchronous gamma oscillations (30 to 80 Hz) hold a special interest in NDDs because of their relation to cortical excitability^{23, 43}, their association with perception and cognition⁴⁴, and measurability in animal models²². The role of gamma oscillations is increasingly nuanced, such that precise synchrony in gamma power is associated with functional networks and higher-order cognition^{36, 45}, but also that a modest degree of asynchrony or "noise" is normal⁴⁶⁻⁴⁸. However, asynchronous (or background) gamma power above what is typically expected has been associated with disordered states⁴⁴ and, at a circuit level, is associated with reduced spike time precision and spectral leakage of spiking activities⁴⁹.

Evidence of Thalamocortical dysfunction:

Alterations in thalamocortical activity may unify the system-level hypothesis that underlies these EEG findings. Thalamocortical dysrhythmia (TCD) is an electrophysiological motif observed in several neuropsychiatric conditions (e.g., epilepsy, Parkinson's disease, tinnitus, depression, and neuropathic pain)⁵⁰⁻⁵² that reflects dysregulated cortical excitability. Like in FXS, patient groups that display TCD exhibit reduced alpha power, increased theta power, increased gamma power, and predominance of theta-gamma CFC. TCD-related EEG alterations have been associated with clinical features in these disorders. Importantly, in our dataset, abnormalities in alpha and gamma power demonstrate significant clinical associations with several core features of FXS, including cognitive function, anxiety, social communication, and auditory attention.

Feasibility of Statistical Learning Tasks (Aim 2): Extensive work by our team ([name]) has reliability demonstrated in infant and youth populations^{31, 53} that neural entrainment of SL can be tracked using EEG (see **Fig. 1C, pg. 13**). To date, SL has not been investigated in FXS, but is a highly salient area of study in FXS given the interest in language acquisition and as a cognitive proxy for learning in youth with FXS^{19, 54}. Furthermore, neural entrainment is amenable to neurodynamic analysis, as embedded words gradually increase as the exposure progresses and predicts improvement in reaction time to test SL performance.

Evidence of neural entrainment by AAE in FXS (Aim 3): To date, neural perturbation, or entrainment to enhance cortical alpha activity, remains unexplored in FXS. The presence of hyperacusis (and EEG evidence of sensory hyperarousal) led the investigative team to consider using rhythmic alpha-frequency auditory signal to modulate cortical activity. We reasoned that an auditory entrainment signal could drive alpha oscillatory activity at both subcortical and cortical levels because encoded acoustic stimuli ultimately reach the temporal lobes via a thalamic intermediary (medial geniculate nucleus). Auditory entrainment has been used effectively as a neural probe, both for short-term suppression of tinnitus^{55, 56} as well as eliciting physiological changes in EEG parameters⁵⁷. Though audio entrainment has mixed evidence for durable effects as a therapeutic modality or cognitive enhancement⁵⁸, it has been shown in some clinical populations to have robust immediate or short-term physiological effects that can be measured by EEG⁵⁹⁻⁶². We hypothesize that enhancement of alpha activity via AAE may activate neural circuits that have an alpha preference, and this enhancement can be observed by increased number of transient alpha spectral events, normalization of sensory auditory chirp response (increased ITC and decreased asynchronous gamma), and enhancement of SL (as measured by increase in word learning ITC). **Closed-loop implementation:** We have integrated AAE into a closed-loop perturbation paradigm in which alpha power can "self- correct" based on real-time responses. Closed-loop perturbation is a powerful framework for testing circuit hypotheses of complex neural phenomena and has emerging use

in clinical settings for epilepsy⁶³, Parkinson's⁶⁴, and Tourette's disorder⁶⁵. A neural closed-loop system would ideally account for individual variability in response by automatically achieving the desired target by modulating the input signal based on empirical feedback⁶⁶.

4.0 Study Endpoints

Aim 1: Sensory Auditory Studies

Primary outcomes of interest: 1) Neurodynamic features (peak power frequency, event rate, event duration), 2) 40 Hz ITC of the sensory auditory chirp, 3) Asynchronous gamma power.

Aim 2: Cognitive Studies

Primary: Word-learning Index (WLI) for the SL passive exposure task, i.e., EEG phase-synchronization at 1.1 Hz (word rate) compared to 3.3 Hz (syllable rate) over the exposure period.

Exploratory: Learning Effect (BLE) of the SL active performance task.

Aim 3: Neural Perturbation Studies

Primary: 1) AAE versus sham change in 40 Hz ITC, and 2) WLI during SL passive exposure task.

Exploratory: AAE vs. sham effect on reaction time (indicated by Behavior Learning Effect) during SL active performance task.

[figure not shown]

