Passive SL Task: Each participant will be presented with both a structured and random stream of syllables. The structured stream will consist of the four generated words, concatenated in pseudorandom order without any pauses or acoustic cues between words (e.g., *vinayfeetidomoo...*). Each word will be presented 200 times, for 800 total word presentations. Order will be constrained to avoid successive syllable and word repeats. The random stream contains the same total number of syllables, which are ordered pseudorandomly to avoid syllable repetitions but will otherwise not follow

any hidden structure. Words will be presented at a rate of 1.1 per a second (thus, syllable rate is 3.3 Hz), resulting in 10 minutes of each structured and random continuous stimuli. As previously published, the expected outcome of this study is an increase in EEG phase-locking at 1.1 Hz over the exposure period—present in the structured condition only—indicative of gradual word discovery and successful word segmentation resulting from statistical learning.

Word-learning Index (WLI) for Passive SL: WLI is the primary EEG outcome measure for the exposure task and, similar to our sensory studies, is based on intertrial phase coherence (ITC). As the participant "learns" the four words in the structured stream (i.e., uses statistical probabilities across neighboring syllables to segregate the speech stream), their EEG typically shows increased phase-locking (increased ITC) at the word presentation rate (1.1 Hz) and decreased phase-locking at the syllable presentation rate (3.3 Hz). Thus, patterns of EEG phase-locking, corresponding to a shift in processing from raw syllable units to cohesive words, reflect gradual statistical learning in the brain. The effect can be quantified by creating a ratio of the ITC for words versus syllables, as follows:

$$WLI = \text{Intertrial Coherence}_{\text{word rate}} / \text{Intertrial Coherence}_{\text{syllable rate}}$$

A higher WLI indicates a relatively stronger response to tri-syllabic nonwords compared to raw syllables, reflecting stronger word segmentation due to statistical learning. The WLI predicts subsequent performance on behavioral tests of statistical learning and increases over time in the structured condition only, and not in the random condition³¹.

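### The 84.3% power claimed for Aim 2 rests on no measured FXS-versus-control WLI effect, and the random stream that would tie WLI to learning has no planned analysis

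*Combined protocol and SAP*

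**What the plan says.** Section 4.0 makes WLI the Aim 2 primary outcome: "EEG phase-synchronization at 1.1 Hz (word rate) compared to 3.3 Hz (syllable rate) over the exposure period". Section 5.2 builds it from inter-trial coherence (ITC): "The effect can be quantified by creating a ratio of the ITC for words versus syllables". The formula has no index for time or stream.

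On the two streams, Section 5.2 says: "Each participant will be presented with both a structured and random stream of syllables". It gives the sign of learning as a WLI that "increases over time in the structured condition only, and not in the random condition". Section 2.0 describes the group comparison this way: "Passive SL Task will compare structured (word) entrainment via EEG intertrial coherence (ITC) between FXS, TDC, and ASD".

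Section 14.0 (Power Analysis) gives two effect sizes. For peak power frequency (PPF), FXS versus TDC, it expects 0.8 to 1.1. For WLI it gives about 0.8, for structured against random. It then names the primary comparisons for Aims 1A and 2 as FXS versus TDC and FXS versus ASD, divides 0.05 by 4, and reports 84.3% power for 40 per group from an effect of 0.8 that it labels FXS versus TDC. It adds that no FXS-versus-ASD effect is available. Section 3.0, on the feasibility of the statistical learning tasks, says such learning has not so far been investigated in FXS.

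Section 14.0 (Statistical analysis) models WLI by diagnostic group with age, sex and non-verbal IQ, further covariates for the ASD comparison, and a group-by-sex term. It has no stream term and no analysis of the random stream.

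**The concern.** There are two separate gaps.

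The first is the power claim. A structured-versus-random difference measures how much listeners learn. An FXS-versus-TDC difference measures how much less one group learns than the other. The first does not supply the second, so for Aim 2 the 84.3% is an assumption presented as if it rested on data. If the true group difference is smaller, a null result could be read as intact learning when the study had little chance of showing otherwise.

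The second is attribution. WLI is a ratio, so it moves when either part moves. A group that follows syllables less well has a smaller denominator and a larger WLI at the same word-rate response. The random stream contains no words, so it shows each child's ratio without learning. It is collected, but the plan does not use it to separate learning from syllable tracking.

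**Working it through.** **1. The plan's own figure.** Inputs from Section 14.0: 40 per group, d = 0.8, alpha = 0.05/4 = 0.0125. Two-sided two-sample t-test, 78 degrees of freedom, critical value 2.557, noncentrality d × √(n/2) = 0.8 × √20 = 3.578. Power is 84.3%, which matches. The arithmetic is not in question.

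**2. What the 0.8 measures.**

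| Outcome | Contrast in Section 14.0 | Effect |
|---|---|---|
| PPF (Aim 1A) | FXS vs TDC | 0.8 to 1.1 |
| WLI (Aim 2) | structured vs random | about 0.8 |
| WLI (Aim 2) | FXS vs TDC | none given |

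The label FXS versus TDC fits only the first row.

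**3. Power when the group effect is an assumption** (same test, 40 per group):

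| d | Noncentrality | Power |
|---|---|---|
| 0.8 | 3.578 | 84.3% |
| 0.6 | 2.683 | 55.2% |
| 0.4 | 1.789 | 22.8% |
| 0.2 | 0.894 | 5.3% |

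**4. Can the WLI 0.8 be converted to a group effect?** Not from the documents, because its scale is not stated. Assume equal SDs and no learning at all in FXS. If the 0.8 is in single-condition SD units, the group d is 0.8. If it is in units of the SD of paired differences, the group d is 0.8 × √(2(1 − r)), where r is the between-stream correlation: 1.13, 0.80 or 0.57 at r = 0, 0.5 or 0.75.

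**5. The ratio.** WLI = W/S, with W the ITC at 1.1 Hz and S the ITC at 3.3 Hz.
- S 20% lower, W unchanged: 1/0.8 = 1.25, so WLI is 25% higher.
- S 20% higher, W unchanged: 1/1.2 = 0.83, so WLI is 17% lower.
- W and S both multiplied by the same factor: WLI is unchanged.

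The effect on a test depends on the SD of log WLI, which the documents do not give. Assume 0.3 to 0.6 and a true word-rate deficit of d = 0.8. With S 20% lower in FXS, the net d is 0.8 + ln(0.8)/SD = 0.06 to 0.43. With S 20% higher, it is 0.8 + ln(1.2)/SD = 1.41 to 1.10.

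**6. What the random stream adds.** All ITC values here are illustrative.

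| | Structured W (mean) | S | Structured WLI | Random W | Random WLI | Structured / random |
|---|---|---|---|---|---|---|
| TDC | 0.15 | 0.40 | 0.375 | 0.10 | 0.25 | 1.50 |
| FXS | 0.125 | 0.333 | 0.375 | 0.10 | 0.30 | 1.25 |

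Structured WLI is the same in both groups although FXS gains half as much over the random stream (0.025 against 0.05). The structured-to-random ratio still shows the deficit. On the log scale, a tracking difference common to both streams cancels.

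**7. Precision of that contrast.** Suppose the group difference is 0.8 in structured WLI and zero in random WLI, with equal SDs. The contrast then has d = 0.8/√(2(1 − r)): 0.57, 0.65 and 0.80 at r = 0, 0.25 and 0.5. Power is 49%, 64% and 84%.

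**The case against.** **The endpoint is largely settled.** Sections 2.0 and 5.2 point to the structured stream, and the formula is one ratio, most naturally taken over the whole exposure. This stands in the main. Section 5.2 does use the same phrase for a rise over time ("the expected outcome of this study is an increase in EEG phase-locking at 1.1 Hz over the exposure period"), so whether WLI is a whole-exposure ratio or a change should be stated, but that is missing detail rather than a contradiction. The phrase word learning ITC in Sections 3.0 and 5.1 is likewise probably loose wording for WLI, which Sections 4.0 and 14.0 both name for Aim 3.

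**The ratio is deliberate.** Section 5.2 expects syllable locking to fall as words are learned, so the denominator carries part of the signal. This stands, and it is a reason to keep the ratio. It also means that a low denominator is ambiguous unless the random stream is examined.

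**The 0.8 may be borrowed from PPF.** It equals the lower end of the Aim 1A range. That would explain the number but would not make it a WLI effect.

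**Stronger readings.** A reader might infer that WLI will hide or reverse an FXS learning deficit. The documents do not support this. They report no 3.3 Hz ITC for FXS, the background statement on imprecise responses concerns the chirp, the bias can run in either direction, and an equal proportional loss at both rates cancels. The illustrations above also leave out the planned covariates. A reader might also infer that a between-group 0.8 requires no learning at all in FXS. That depends on the scale: on a paired scale with r = 0, FXS could keep 1 − 0.8/1.13 = 29% of the learning effect and still differ by 0.8.

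**Conclusion.** Two parts hold on the text alone. The 84.3% is correctly computed and supported for PPF in Aim 1A, but for the Aim 2 group test it rests on no between-group WLI effect. Across d from 0.8 to 0.2, power runs from 84% to 5%, and nothing in the documents places the true value within that range. In addition, the random stream has no analysis in the Aim 2 models, so neither a WLI group difference nor its absence can be attributed to statistical learning rather than to 3.3 Hz tracking.

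The size and direction of any tracking bias are unknown. The 25% figure is arithmetic for an assumed 20% difference, not an estimate for FXS. The case for making the group-by-stream contrast primary is not made either: it could reduce power to 49% if the streams are uncorrelated. This should be corrected before analysis. It does not invalidate the outcome or the data collection.

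**What to change.** 1. **Section 14.0, Power Analysis.** State that the WLI 0.8 is a structured-versus-random effect and not a between-group one. Give Aim 2 power as an assumption over a range of d, for example 84%, 55%, 23% and 5% at 0.8, 0.6, 0.4 and 0.2. This costs wording only.

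2. **Section 14.0, Statistical analysis.** Keep structured-stream WLI as the Aim 2 primary. Add a prespecified supporting group-by-stream contrast on log WLI, and report 1.1 Hz and 3.3 Hz ITC by group and stream. Attribute a WLI group difference, or its absence, to statistical learning only if the contrast estimate and its confidence interval are consistent with that. Both streams are already presented ("resulting in 10 minutes of each structured and random continuous stimuli"), so no new data are needed. The cost is a little more analysis and a contrast that is less precise when the streams correlate weakly. The contrast does not remove everything: stream order is not stated, fatigue could differ between streams, and syllable locking itself changes with learning.

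3. **Sections 4.0 and 14.0.** In the same edit, say that WLI comes from the structured stream and whether it is the whole-exposure ratio or a change over exposure.

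The time allowed per Aim 3 segment in Section 5.2, against the length of the two streams, is a separate matter to reconcile.
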